6.3. Protocol Deviations

As described in Section 4.2, subjects who fail to meet any of the inclusion/exclusion criteria will be tabulated and listed by treatment group for FA Population. This will be based on data recorded on the inclusion/exclusion page of the eCRF. A separate listing or summary (if applicable) of significant protocol deviations (described in Section 4.2) will be generated.

6.4. Demographic and Baseline Characteristics

Continuous variables such as age, body mass index, weight, and height will be summarized using descriptive statistics (n, mean, standard deviation, median, minimum, and maximum). Categorical variables including age group (<65, \geq 65 years), sex, race, ethnicity, baseline HbA_{1c} category (<8%, \geq 8%), and current metformin use (yes, no) will be summarized using numbers and percentages. Summaries will be presented by treatment group using the FA Population and Safety Population.

Summary of substance (alcohol and tobacco) use will be provided, as well as a by-subject listing of data on alcohol and tobacco use. All summaries will be performed using the FA Population.

6.5. Exposure to Study Drug

Descriptive statistics including the number of subjects, mean, standard deviation, median, minimum, and maximum for the duration of study drug exposure to the treatment received will be presented by treatment group for the Safety Population. The duration of study drug exposure is defined as date of last dose of randomized study drug - date of first dose of randomized study drug + 1. The total person time on treatment (in years) as defined in [Appendix 5](#) will also be displayed for each treatment group.

Additionally, the prescribed total daily dose of insulin glargine and insulin lispro will be tabulated by visit.

A by-subject listing of study drug administration will also be presented.

6.6. Treatment Compliance

Investigational product accountability will be done for albiglutide at each study visit after the baseline visit through the end-of-treatment visit (Visit 9, Week 26).

Albiglutide treatment compliance will be calculated as total number of doses administered divided by total number of doses expected based on the last dose date at the end of active treatment period. Total number of albiglutide administered during the treatment period will be computed as the number of expected dose minus the number of missed dose. For the number of expected dose, if subject completes the treatment, it will be 26. If subject doesn't complete the treatment, the number of expected dose will be equal to the number of weeks between treatment start date and treatment end date. The number of missed dose information, treatment start and end date are captured on the albiglutide administration CRF page. Treatment compliance will be summarized for all subjects, as well as for subjects who discontinue treatment early and subjects who complete active treatment. Summary statistics for treatment compliance percentages, as well as the number and percentage of subjects who are $<80\%$ and $\geq 80\%$ compliant will be reported for the Safety Population. Individual subject compliance information will also be listed.

Treatment compliance of subjects for insulin glargine and insulin lispro will be assessed by the investigator at each visit and reported on the eCRFs. At each visit on or after baseline, the investigator will answer "yes/no" to the question of "Do you believe the subject has been compliant with their insulin regimen at least 80% of the time". If the investigator answered "yes" for all the postbaseline visits for treatment compliance assessment (Week 4, 10, 18, and 26), the subject will be considered as being $\geq 80\%$ compliant to the treatment during the entire study period. For subjects who discontinued the study early, the same rule will apply and the assessment of overall compliance will be based on the data from the completed visits. The number and percentage of subjects in each compliance category will be summarized overall and by study visit for the safety population. Individual subject compliance information will be listed.

Acceptable overall compliance for IP (albiglutide) and other study treatments (insulin glargine and insulin lispro) in this study will be $\geq 80\%$.

6.7. Dose Titration and Insulin Lispro Re-introduction

The albiglutide dose in this study will start at 30 mg weekly and be titrated to 50 mg weekly at Week 4.

Both treatment arms will follow the same insulin glargine titration algorithm during the Standardization and Treatment Periods (see Table 3 of the Protocol).

Both treatment arms will follow the same insulin lispro titration algorithm during the standardization period. At randomization, the start of the treatment period, the insulin lispro titration algorithm will be individualized for each treatment arm (see Table 4 of the protocol).

Insulin lispro may be re-introduced after Week 8 for subjects in the albiglutide treatment group. The number of subjects for whom insulin lispro was re-introduced will be summarized. For these subjects, the re-introduced insulin lispro will be characterized in terms of the number of injections and the total dose over time. The dosing guidance for albiglutide, insulin lispro, insulin glargine, and metformin treatment can be found in Table 2 of the Protocol.

Individual dose titration information and insulin lispro re-introduction will be listed for the safety population.

For lispro re-introduction through Week 26, it will include lispro re-introduced up to Week 25 and not include lispro prescribed at Week 26. This is due to that the last albiglutide injection is given at Week 25 for subjects in albiglutide arm and at Week 26 lispro may be prescribed as per standard of care.

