Should a subject fail to attend the clinic for a required study visit, the site should attempt to contact the subject and reschedule the missed visit as soon as possible. The site should also counsel the subject on the importance of maintaining the assigned visit schedule and ascertain whether or not the subject wishes to and/or should continue in the study based on previous noncompliance. In cases where the subject does not return for the

rescheduled visit or cannot be reached to reschedule the missed visit, the site should make every effort to regain contact with the subject (3 telephone calls and if necessary a certified letter to the subject's last known mailing address) so that they can appropriately be withdrawn from the study. These contact attempts should be documented in the subject's medical record. Should the subject continue to be unreachable, then and only then will he/she be considered to have withdrawn from the study with a primary reason of "Lost to Follow-up." For all other subjects withdrawing from the study, an alternative reason for discontinuation should be recorded in the eCRF.

The half-life of albiglutide is approximately 5 days, and significant therapeutic concentrations can persist for 3 to 4 weeks after discontinuation. Therefore, the investigator should use caution when prescribing treatment after the withdrawal of active study medication, taking into consideration the long half-life of albiglutide. Thereafter, postwithdrawal treatments may be modified over time, as needed, at the investigator's discretion.

Study medication withdrawal will require withdrawal from the study. Withdrawn subjects will not be replaced.

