5.7.1. Treatment Between Week 26 (End of Treatment)/Early Withdrawal and Follow-up

After completion of the end-of-treatment (Week 26) or early withdrawal visits, subjects will return to the study center in 4 weeks for the Follow-up visit. During this time, subjects will continue insulin glargine or insulin glargine plus insulin lispro to maintain adequate glycemic control.

For subjects in the albiglutide plus insulin glargine treatment arm, the last dose of once-weekly albiglutide will occur at Week 25. As needed, insulin lispro may also be re-introduced during this period according to the re-introduction of insulin lispro algorithm provided in Section 5.1.3.5. Insulin glargine alone (in subjects for whom insulin lispro has not been re-introduced) or insulin glargine and insulin lispro (in subjects for whom insulin lispro has been re-introduced) can be adjusted to achieve or maintain glycemic targets as close to normal as possible without untoward hypoglycemia

in accordance with product labeling in the respective country and standards of care at the study center.

For subjects in the insulin glargine plus insulin lispro treatment arm, both insulin glargine and insulin lispro may be adjusted to achieve or maintain glycemic targets as close to normal as possible without untoward hypoglycemia in accordance with product labeling in the respective country and standards of care at the study center.

Note: During this time, subjects must not use any prohibited medications or nondrug therapies (see Section [5.6.2](#)).

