4. ANALYSIS POPULATIONS

Population	Definition / Criteria	Analyses Evaluated
Full Analysis (FA)	
 • Comprise of all subjects randomly assigned to treatment. • Randomly assigned subjects who do not receive any study treatment will also be included. • The subjects in the FA Population will be analyzed according to randomized treatment. 	
 • Study Population • Efficacy
Per-Protocol (PP)	
 • Comprise of all randomized (FA Population) subjects who complete study procedures through Week 26 or beyond. • The subjects in the PP Population will be analyzed according to randomized treatment. 	
 • Supportive Efficacy Analysis
Safety	
 • Include all subjects who receive at least 1 dose of randomized study medication. • The subjects in the Safety Population will be analyzed according to the treatment received. 	
 • Safety • Study Population

NOTES :

- Please refer to Appendix 14: List of Data Displays which details the population to be used for each displays being generated.

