8.1.2. Key Secondary Efficacy Endpoints

8.1.2.1. Proportion of Subjects Who Do Not Meet Prespecified Criteria for Severe, Persistent Hyperglycemia through Week 26

For this key secondary endpoint, subjects who do not meet prespecified criteria for severe, persistent hyperglycemia through Week 26 will be defined operationally as those subjects treated with once-weekly albiglutide that are able to replace prandial insulin without lispro re-introduction through Week 26. Note: For lispro re-introduction through Week 26 the time window is defined up to Week 25.

Proportion of subjects that are able to discontinue insulin lispro at Week 4 and do not meet prespecified criteria for severe, persistent hyperglycemia through Week 26 will be summarized descriptively for all the Albiglutide + Insulin Glargine arm subjects and for

subgroups of baseline HbA_{1c} category (<8.0%, ≥8.0%), region, (<65 years versus ≥65 years), current use of metformin (Yes, No) in the FA population. The 95% confidence interval of the proportions of subjects will be provided.

The insulin lispro that was re-introduced to albiglutide subjects will be characterized. Summary statistics for the number of injections, total dose, and time-to-re-introduction will be presented.

Additional exploratory analyses to identify potential risk factors for lispro re-introduction will be investigated. Potential risk factors include: baseline HbA_{1c}, baseline HbA_{1c} category, age, age category, metformin-use, duration of diabetes, weight, BMI, BMI category, time in insulin (at baseline), baseline HbA_{1c}, and total insulin dose at baseline. Time in insulin (at baseline) is defined as the earliest start date of prior insulin medications taken minus the date of first date of randomized study medication, plus 1.

8.1.2.2. Percentages of Subjects with Severe or Documented Symptomatic Hypoglycemia through Week 26

The percentage of subjects with severe or documented symptomatic hypoglycemia will be summarized descriptively by treatment and analyzed using a Cochran-Mantel-Haenszel (CMH) test, stratified by baseline HbA_{1c} category, region, age category (<65 years versus ≥65 years), current use of metformin (Yes, No) in the FA population.

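### SAP 8.1.2.1 can count early leavers with no lispro recorded as having replaced prandial insulin through Week 26, and the Week 25 window ignores each subject's own last albiglutide dose

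*SAP*

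**What the plan says.** SAP 8.1.2.1 defines success operationally as "subjects treated with once-weekly albiglutide that are able to replace prandial insulin without lispro re-introduction through Week 26", and adds "For lispro re-introduction through Week 26 the time window is defined up to Week 25". SAP 6.7 states the same window ("For lispro re-introduction through Week 26, it will include lispro re-introduced up to Week 25 and not include lispro prescribed at Week 26"). Its reason is that a completer's last albiglutide injection is at Week 25, after which "at Week 26 lispro may be prescribed as per standard of care".

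The proportion is reported for the albiglutide arm of the Full Analysis population, for which SAP 4 says: "Randomly assigned subjects who do not receive any study treatment will also be included". SAP 8.1.2.1 also plans summaries of number of injections, total dose and time to re-introduction, and an exploratory search for risk factors.

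On early leavers, Protocol 4.5 says "Study medication withdrawal will require withdrawal from the study". Protocol 5.7.1 then says "After completion of the end-of-treatment (Week 26) or early withdrawal visits, subjects will return to the study center in 4 weeks for the Follow-up visit". For the albiglutide arm it adds "As needed, insulin lispro may also be re-introduced during this period".

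**The concern.** Two separate gaps follow.

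**Success does not require presence.** It is the absence of a recorded event, in a population that keeps everyone randomized. A subject who leaves at Week 12 without lispro on record has no event. Nor does one who leaves at Week 6, after lispro stops at Week 4 but before Protocol 5.1.3.5 permits re-introduction (after Week 8). That second subject could not have had the event under the protocol while on albiglutide. Both can be counted as having replaced prandial insulin through Week 26.

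**The window is a study week, not a last dose.** The SAP's reason for stopping at Week 25 is that lispro given after albiglutide ends is ordinary care. For a subject who stops at Week 12 the same reasoning would apply 13 weeks sooner, but the rule still runs to Week 25. Lispro first prescribed on leaving is then counted as re-introduction and feeds the planned timing, dose and risk-factor summaries.

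This endpoint most directly measures what the trial is about. As written, part of its value depends on how long subjects stayed and what was recorded after they stopped.

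**Working it through.** **1. Planned number of early leavers.** Inputs from Protocol 8.2.1 and SAP Appendix 12: margin 0.3, SD 1.2, true difference 0, one-sided 0.025, 90% power, 15% early withdrawal.

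- Completers per arm: 2 × (1.960 + 1.282)² × 1.2² / 0.3² = 336.2, so 337. This matches the plan (noncentral t power at 337 is 0.8998).
- Randomized per arm: 337 / 0.85 = 396.5, so 397, or 794 in total. This matches the plan.
- Early leavers in the albiglutide arm: 397 − 337 = 60, or 15.1%.

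**2. Where post-stop records fall.** SAP 11.3.4 targets the follow-up visit of an early leaver at last dose + 35 days, i.e. 5 weeks. A last dose at Week 12 puts follow-up at about Week 17. A last dose at Week 20 puts it at about Week 25. For last doses up to about Week 20, all follow-up lies inside the Week 25 window.

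**3. Whether another rule closes the gap.**

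- SAP 11.3.4 uses the visit and date on the eCRF for prescribed-insulin analyses, so study-day slotting does not clearly remove these records.
- SAP 11.3.3 accepts an end-of-treatment visit up to 14 days after last dose as valid efficacy data.
- SAP 8.1.3.3 has a reason-specific rule for missing Week 26 HbA1c, but only for the HbA1c targets.
- Table 2.43 repeats the hypoglycemia analysis without early withdrawals. Table 2.31, for this endpoint, has no counterpart.

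**4. Effect on the headline proportion.** Let k be the early leavers with no lispro recorded in the window. Read literally they are successes; under the fix below they are not. The difference is k/397, whatever the completers' success rate. Leavers already re-introduced on albiglutide, and leavers first given lispro after stopping, are non-successes either way and contribute nothing.

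- Upper bound, k = 60: 60/397 = 15.1 points.
- Adverse-event withdrawals only, at the 5% albiglutide-arm rate that SAP 11.6.3.2 cites from an earlier study: 0.05 × 397 ≈ 20, and 20/397 = 5.0 points.
- If overall early withdrawal were 10% or 20%: 40/397 = 10.1 or 79/397 = 19.9 points at most.

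**5. Against sampling error.** The documents give no expected success rate, so completer rates of 50%, 70% and 90% are assumed. The half-width is 1.96 × √(p(1−p)/397), evaluated at the same p.

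| Assumed completer success | All 60 leavers non-success | All 60 leavers success | 95% CI half-width |
|---|---|---|---|
| 50% (168/337) | 168/397 = 42.3% | 228/397 = 57.4% | 4.9 points |
| 70% (236/337) | 236/397 = 59.4% | 296/397 = 74.6% | 4.5 points |
| 90% (303/337) | 303/397 = 76.3% | 363/397 = 91.4% | 3.0 points |

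The worst case is about 3 to 5 times the half-width. The adverse-event-only case is about 1 to 1.7 times.

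**The case against.** **The SAP is silent, not wrong.** It never says early leavers are successes, and a careful programmer could read being able to go without lispro through Week 26 as requiring the subject to be there. That is fair. But the only operational test written down is absence of re-introduction, and an unstated choice should not settle a key secondary result.

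**The Week 25 cut does not drive the headline.** A leaver given lispro after stopping is a non-success with or without the cut. This stands: moving the window corrects the re-introduction count and the descriptive summaries. The proportion changes only through the missing rule for leavers with no lispro recorded.

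**Early Withdrawal can be treated like Week 26.** The protocol pairs the two visits, so lispro prescribed at the Early Withdrawal visit might be excluded by analogy. That would be sensible, but neither SAP section says so.

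**Albiglutide is still active after the last dose.** SAP 5.5 treats last dose + 25 days as on therapy, so lispro at a prompt Early Withdrawal visit is normally inside that period. This is true, and it would be too strong to call all such lispro off-treatment. However, a completer's Week 26 visit is only 7 days after the Week 25 dose, also inside 25 days, and the SAP excludes lispro prescribed there. For this endpoint the SAP's own dividing line is the last dose.

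**Counting leavers as non-success is one estimand among several.** Agreed, which is why a completers-only version belongs beside it. Subject listings would let the sponsor check the figure, but they do not prespecify it.

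**Conclusion.** The point holds. SAP 8.1.2.1 lets early leavers with no lispro recorded count as having replaced prandial insulin through Week 26, and SAP 6.7 applies its reason for the Week 25 cut to completers only. The likely direction is an overstated proportion, and the re-introduction summaries mix on-treatment need with prescribing after albiglutide stopped. The change is worth making before analysis, but the trial does not stand or fall on it.

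A reader might infer more than the documents support:

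- *A 15-point bias is expected.* It is a ceiling. It takes all 60 planned leavers whatever their reason and assumes none had lispro recorded. Some will have been re-introduced on albiglutide, and those gone before Week 4 also turn on the separate requirement to discontinue lispro at Week 4. The one cause-specific rate in the documents gives about 5 points; procedural withdrawals would add an unknown amount.
- *The trial's main conclusion is at risk.* It is not. SAP Appendix 10 treats this endpoint as single-arm with no treatment comparison and leaves it out of the testing sequence. The noninferiority result and type I error are unaffected.

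No view is taken on when lispro should be prescribed. The issue is only how prescriptions and departures are counted.

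**What to change.** In SAP 6.7 and 8.1.2.1:

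1. End the analysis window for re-introduction at the earlier of Week 25 and the subject's last albiglutide dose. Apply this to the count and to the timing, dose and risk-factor summaries.
2. In Table 2.31, count as success only subjects still on albiglutide and without lispro at Week 25.
3. Report early leavers without on-treatment re-introduction in a separate did-not-complete row, counted as non-success in the headline proportion.
4. Add an observed-data or completers-only version as a sensitivity analysis.

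A Kaplan-Meier estimate of time to re-introduction, censored at last albiglutide dose, is optional.

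The cost is a few sentences of SAP text and one extra summary. SAP Appendix 4 already takes last albiglutide dose dates from the exposure data set, and SAP 6.8 places prescribed lispro on the Insulin Surveillance eCRF page, so no new data and no change to treatment are needed. The downside is that the headline proportion may be lower.

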6.8. Medications

Any prior and concomitant medication used during the study will be recorded and coded using GSKDRUG dictionary, which will be updated whenever available throughout the life of the study. Summary of all medications by treatment group and preferred term will be provided in relation to treatment phase (prior medication, concomitant medication, or post-therapy medication). Prior medications are those started and stopped before the first dose of randomized study drug. Concomitant medications are those taken at any time on or after the day of the first dose of randomized study drug and within last dose date plus 25 days in the albiglutide arm or within the last dose date in the lispro arm, including those medications that started prior to randomization and continued into the treatment period. Post-therapy medications are those taken after last dose date plus 25 days in the albiglutide arm or after the last dose date in the lispro arm.

For this study, insulin glargine, insulin lispro and any other anti-hyperglycemic medications will be recorded through screening period on the concomitant medications eCRF pages. Once subjects enter Visit 2 (Standardization Week -4 visit), the prescribed dose for insulin glargine and for insulin lispro are captured in the Insulin Surveillance eCRF page.

All prior and concomitant medications will be listed using generic and verbatim terms. All summaries will be performed using the safety population.

6.9. Medical History

Subject data listings and summary tables will be provided for the following current and/or past conditions:

- cardiovascular medical history
- diabetes history
- medical/surgical procedure history
- gastrointestinal (GI) medical history

- nephropathy (including microalbuminuria) and kidney injury history
- diabetic retinopathy history
- cancer history
- pneumonia medical history
- skin medical conditions
- thyroid history, thyroid cancer history
- history benign thyroid conditions
- thyroid cancer family history
- pancreatitis family history
- pancreatic cancer family history
- other medical history

The number and percentage of subjects with current and/or past cardiovascular medical history will be reported by treatment group. Also, the number and percentage of subjects with current and/or past diabetes history will be tabulated by treatment group. A summary of duration of diabetes disease history in years will be provided. The duration of diabetes disease history is calculated as the years lapsed between screening visit date and T2DM diagnosis date.

The number and percentages of subjects with current and/or past medical/surgical procedure history, gastrointestinal (GI) medical history, nephropathy (including microalbuminuria) and kidney injury history, diabetic retinopathy history, cancer history, pneumonia medical history, skin medical conditions, thyroid history, thyroid cancer history, history benign thyroid conditions, thyroid cancer family history, pancreatitis family history, pancreatic cancer family history and other medical history will be presented in a similar manner as described for cardiovascular medical history.

In addition, by subject listings of medical and family history status and all the medical conditions listed above will be provided.

All summaries will be performed using the safety population. In the case of scarce data for a medical history and summary is not necessary, only a listing will be provided.

